In sensitivity analysis, we will vary this timeframe to define surveillance frequency based on the timing of the first PSA test following completion of prostatectomy or radiation therapy (first PSA within 3 months vs. >3 but within 6 months vs. >6 months); or define comparison groups empirically (most frequent 1/3 of patients vs. middle vs. least frequent 1/3 of patients) – to assess if our findings are robust to these varying exposure groupings [IR-5]. We will also explore using Years 1-2 to define surveillance frequency, and examining patient outcomes from Years 3-10.

Figure 1. Sample Identification and Definition of Timeframes for Measurement

Data Source [IR-1][DR-2][PC-2]: The National Cancer Data Base (NCDB) is a joint program between the Commission on Cancer (CoC) of the American College of Surgeons and the American Cancer Society.⁸ NCDB, started in 1989, is a nationwide cancer outcomes database that includes $>1,400$ CoC-accredited cancer programs and $\sim 70\%$ of all newly diagnosed cancer cases in the US – making its data broadly generalizable and ideal for CER.⁸⁻¹⁰ Systematic, longitudinal follow-up data are updated annually, with multiple data-quality assurance steps taken. **The high quality and representative NCDB data are used for the annual US “cancer statistics” report.**^{11,12} Thus, our results using the NCDB optimizes external validity and generalizability. Data elements are recorded by certified cancer registrars using nationally standardized data item and coding definitions specified by the Facility Oncology Registry Data Standards. Detailed information about data elements collected by the NCDB, standardized data collection protocol, and quality control methods used to assess reported case information is available at: www.facs.org/cancer/ncdb/datasubmission.html.

NCDB Special Study mechanism for primary data collection will be used to obtain the detailed level of information required for this study on data elements which do not currently exist in the NCDB registry – including PSA frequency – and to fill in missing data [MD-1].¹³⁻¹⁵ This will be done using chart abstraction by each of the CoC-accredited centers. For this Aim, the NCDB will randomly select 10 prostate cancer patients diagnosed in 2005-07 from each CoC-

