accredited center, with purposeful sampling in order to achieve approximately the same overall sample size in each of the 6 risk group x treatment cohorts. By randomly selecting a small number of patients from a large number of institutions, we can ensure a broadly representative sample of hospitals and patients, ideal for CER.

Outcomes [RQ-6]: The NCDB annually collects vital status (survival), cancer status (disease free or recurrence), date of recurrence, and treatments for recurrent cancer. This will allow for evaluation of our primary outcome of overall survival, and secondary outcomes of time to recurrence and treatment for recurrent cancer. Additional secondary outcomes will be collected by the special studies mechanism, and include: rates and types of procedures (e.g. biopsy) and tests (e.g. advanced imaging), results of these tests, and treatment for recurrent cancer.

The special studies mechanism will also confirm existing NCDB information regarding cancer status and date of recurrence. Specifically, the PSA dates and results will be abstracted from medical records. Therefore, the investigators are able to define recurrence per standard definitions. These citations provide official definitions for biochemical recurrence after radiation treatment¹⁶ and radical prostatectomy.¹⁷

Cancer registry staff will review hospital and provider records to collect these data, using the same rigorous procedures as primary registry data with specific instructions and training for abstraction by the investigative team and personnel at CoC. These data will be combined with the existing NCDB data to provide the analysis dataset. This Table summarizes the data elements (outcomes) to be collected using the special studies mechanism: (Table 1)

Data Point	Format
Date of imaging	mm/dd/yy
Type of imaging performed	1) bone scan; 2) CT scan; 3) MRI; 4) X-ray; 5) PET scan; 6) other
Date of biopsy/procedure	mm/dd/yy
Biopsy/procedure results	1) benign; 2) malignant; 3) indeterminate
Date of treatment for recurrence	
Type of treatment	1) radiation; 2) surgery; 3) hormone therapy; 4) chemotherapy; 5) other therapy; 6) no treatment

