The analysis is stratified by two important factors, risk of recurrence (low, intermediate, high) and type of initial treatment (surgery, radiation); thus, 6 separate analyses will be performed. All outcomes will be defined from years 2-10 from end of prostatectomy or radiation treatment (Figure 1). We will use two modeling strategies to evaluate our outcomes of interest: 1) modified Poisson/binary regression^{19,20} with sandwich standard errors to estimate risks of the events of interest during a set follow-up period; and 2) Cox Proportional Hazards regression [CI-3]. Using the modified Poisson/binary regression models, we will estimate the risk of experiencing the outcome of interest (death, recurrence, use of procedures and tests, treatment for recurrence) during a defined interval beginning in the second year following treatment. Additionally, we will estimate overall survival using adjusted Cox Proportional Hazards regression models. We will evaluate the proportional hazards assumption by generating Kaplan-Meier survival curves and through testing interactions between relevant covariates and time in the Cox model. Covariates that violate the proportional hazards assumption will be used as stratification variables as appropriate. In sensitivity analyses, we will generate a propensity score (where the patient, provider and hospital characteristics measured at the time of prostatectomy or radiation completion are included in the propensity score) and create a matched cohort of patients to evaluate using Kaplan-Meier survival models [described in detail in C3]. For secondary outcomes, time to recurrence will be modeled for each surveillance frequency using a competing risk analysis as described by Fine and Gray.²¹ Similar methods will be used to calculate the cumulative incidence of procedures and tests and treatment for recurrence.

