Several outside/environmental factors can affect a patient's surveillance frequency. In our preliminary analysis using the US population-based Surveillance, Epidemiology and End Results (SEER)-Medicare dataset, we found race, marital status, and regional socioeconomic determinants (high school graduation rate) to be associated with different PSA surveillance frequencies. The NCDB captures a comprehensive list of covariates (see above). We will examine if surveillance frequency is associated with each individual factor and account for these factors using modeling as above. Finally, we recognize that there may still be important unmeasured confounders in our study; therefore, we plan to use sensitivity analyses to estimate the impact of a hypothetical unmeasured/unobserved confounder, using similar methodology used in a prior study by the co-I ([name]).²² This analysis will allow us to determine the extent of confounding that would substantively change our study findings.

A conceptual diagram (directed acyclic graph) demonstrating the relationship between measured covariates and our selected study outcomes for Aim 1 is provided in Figure 2 below.

Figure 2. Directed Acyclic Graph for the Hypothesized Relationship between Selected Study Variables and Outcomes for Aim 1

Footnote: Analyses will be stratified by the type of initial treatment (surgery, radiation) and recurrence risk (low, intermediate, high) and the hypothesized relationships may vary somewhat by each clinical scenario. Relationship between variables identified as pertaining to Aim 2 are noted in Figure 3.

Statistical power: There are >1,400 CoC-accredited hospitals. With 10 patients sampled at each hospital, we expect 14,000 patients will be available for analysis. We will intentionally sample approximately the same number of patients in each of the 6 cohorts (risk group x primary treatment), providing 2,333 patients in each cohort. Within each cohort, patients receiving different surveillance frequencies will be compared. Based on preliminary analysis of SEER-Medicare data, the national patterns of PSA surveillance in the first year are: (Table 2)

Number of PSAs	Low Risk	Intermediate Risk	High Risk
1	20%	18%	17%
2-3	61%	59%	53%
4	19%	23%	30%

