Patients treated within a site may be more similar with regard to surveillance frequency than patients treated within other sites. Given this, we will evaluate the need for clustering patients within sites by estimating the variance in surveillance frequency and outcomes within versus between sites. If clustering is indicated we will incorporate a site level term into our regression models as 1) a grouping variable; 2) as a fixed effect within the regression model (to control for time-invariant omitted variables and methodological artifacts of temporal correlation), and 3) as a random effect (to control for unobserved heterogeneity which may be constant over time and correlated with independent variables). These analyses will be in addition to the analytic techniques previously proposed (propensity score and instrumental variables methods), which provide alternative approaches to examining for these issues, and are discussed in C3. If the variation between clusters is small, we will present regression results without clustering (focused on patient-level analyses) for our primary analytic strategy.

We will assess the prevalence of patients receiving treatment before meeting official definition of recurrence, and whether this prevalence is similar or different in the comparison groups. In our primary analysis, we will assess outcomes (procedures, treatments) regardless of whether patients received treatments before meeting official definition of recurrence – because this is likely the result of patient/physician anxiety caused by frequent PSA surveillance testing. However, in sensitivity analysis, we will exclude patients who received treatment before meeting official definition of recurrence.

C2. Specific Aim 2: Compare patient-reported outcomes in prostate cancer survivors followed with alternative surveillance frequencies.

Hypothesis: More frequent surveillance is associated with more patient-reported anxiety and worse health-related quality of life.

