Statistical power: A total of 1,079 participants have completed MAX-PC (primary outcome), PCSI and SF12 (secondary outcomes) at 12 months. If there is attrition of 25% from 12 to 60-month time points, that leaves N=809 with complete data. Using the distributions in Table 2, this sample size provides >90% power to detect a $\frac{1}{2}$ -standard deviation (clinically significant) difference in anxiety among the different surveillance frequency groups. More specifically, a sample size as small as 154 in each group will provide 90% power to detect $\frac{1}{2}$ -standard deviation difference among groups. For secondary outcomes PCSI and SF-12, assuming a standard deviation of 10,^{36,37} we have >90% power to detect clinically meaningful differences (1/2 standard deviation = 5 points) among groups. All $\alpha=.05$; two-sided tests.

Potential problems and alternative strategies: Patients with different baseline HRQOL and anxiety may receive different surveillance frequencies. The longitudinal design of Aim 2 and availability of pre-treatment data allow us to analytically account for these potential differences among comparison groups. We do not have MAX-PC data pre-treatment, but will examine if pre-treatment anxiety (an item on SF-12) differs by surveillance frequency groups. If so, we will adjust for this baseline anxiety measure in data analysis. We will address potential clustering as described on Page 6.

We will evaluate the extent to which attrition impacts our analysis and subsequent interpretation. We have planned multiple sensitivity analyses to ensure the robustness of our findings, including

evaluations of the impact of a hypothetical unmeasured confounder, instrumental variables analysis, stratification and restriction.

C3. Avoidance of bias [IR-3][GM-3][CI-5][CI-6]: The large population cohorts used in Aim 1 and Aim 2 will provide a high level of evidence from real-world settings. The following analytic methods to minimize bias and confounding are consistent with the PCORI Methods Report (“Standards for Causal Inference Methods,” dated 3/15/12) and the recent AHRQ publication, “Developing a Protocol for Observational Comparative Effectiveness Research, A User’s Guide.”

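### Aim 1 may drop hospital clustering from its primary analysis on an undefined judgement that between-site variation is small; intervals could be slightly too narrow, and the correction is almost free

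*Combined protocol and SAP*

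**What the plan says.** The Data Source section of Aim 1 makes the hospital the sampling unit: "the NCDB will randomly select 10 prostate cancer patients diagnosed in 2005-07 from each CoC"-accredited center. It gives the reason as representativeness: "By randomly selecting a small number of patients from a large number of institutions". The Statistical power section repeats the design ("With 10 patients sampled at each hospital, we expect 14,000 patients will be available for analysis") and divides the sample equally, "providing 2,333 patients in each cohort". The Data Analysis section stratifies by risk and initial treatment: "thus, 6 separate analyses will be performed".

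The clustering rule is in Potential problems and alternative strategies for Aim 1. It expects possible similarity within sites and plans to compare within-site with between-site variance, for surveillance frequency and for outcomes. If clustering is indicated, site enters as a grouping variable, a fixed effect and a random effect. Otherwise: "If the variation between clusters is small, we will present regression results without clustering".

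The modified Poisson models have sandwich standard errors, but the plan does not say that these are clustered by site. No robust variance is mentioned for the Cox models. Aim 2 borrows the same rule: "We will address potential clustering as described on Page 6".

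**The concern.** Because patients are drawn hospital by hospital, dependence within a hospital is a feature of the design. It does not need to be established by a preliminary look at the data.

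The rule also leaves several things open:
- how small is small;
- whether surveillance frequency, the outcome or both must show little variation;
- whether the check is made per cohort or on all patients together;
- which of the three site models would be primary if clustering is indicated.

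The primary variance estimator is therefore chosen after the data are seen. If the check misses a real correlation, the error runs towards intervals that are too narrow, provided that surveillance frequency and outcome both vary by site. The plan itself makes the first plausible: C3 proposes region and provider preference as instruments because they are expected to predict surveillance frequency.

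**Working it through.** **Inputs from the documents.** More than 1,400 hospitals (1,400 used below), 10 patients each, six cohorts analysed separately, two-sided alpha 0.05. The plan's own figure reproduces: 1,400 × 10 = 14,000, and 14,000 / 6 = 2,333 per cohort.

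**Assumptions.** The documents give no ICC. I take an outcome ICC of 0.05 as the main case and let the exposure ICC (how far the site sets surveillance frequency) run from 0.2 to 1.

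**Step 1: patients per hospital within a cohort.** The plain mean is 2,333 / 1,400 = 1.67. The design effect depends on the size-weighted mean. If the 10 patients fall at random over six cohorts, this is 1 + 9/6 = 2.5. I use both, since 1.67 is a floor.

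**Step 2: can the check see the correlation?** Each hospital has 10 × 9 / 2 = 45 pairs of patients, and a given pair falls in one given cohort with probability 1/36. Same-site pairs per cohort: 1,400 × 45 / 36 = 1,750. The standard error of a small ICC is about 1/√1,750 = 0.024. Taking a one-sided 5% test as the rule (also an assumption), the chance of missing a true ICC is Φ(1.645 − ICC/0.0239):
- ICC 0.02: 79%
- ICC 0.05: 33%
- ICC 0.10: 0.6%

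With all 14,000 patients together there are 1,400 × 45 = 63,000 pairs, the standard error is about 0.004, and an ICC of 0.05 would not be missed.

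**Step 3: effect on the interval.** For a comparison of surveillance groups, the design effect is about DE = 1 + (m − 1) × ICC_exposure × ICC_outcome. The unclustered interval is too narrow by 1 − 1/√DE, and its type I error is 2 × [1 − Φ(1.96/√DE)]. At an outcome ICC of 0.05:

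| Exposure ICC | m = 1.67: DE; too narrow by; type I error | m = 2.5: DE; too narrow by; type I error |
|---|---|---|
| 0.2 | 1.007; 0.3%; 5.1% | 1.015; 0.7%; 5.2% |
| 0.5 | 1.017; 0.8%; 5.2% | 1.038; 1.8%; 5.4% |
| 1 (ceiling) | 1.033; 1.6%; 5.4% | 1.075; 3.6%; 5.9% |

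**Step 4: simulation of one cohort** (1,400 sites, 3,000 runs, so a Monte Carlo error of about 0.4 points on each rate):

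| Exposure ICC / outcome ICC | Type I error, unclustered | Type I error, site-clustered | Ratio of standard errors |
|---|---|---|---|
| 0.2 / 0.05 | 5.0% | 5.0% | 1.007 |
| 0.5 / 0.05 | 5.3% | 4.8% | 1.017 |
| 0.8 / 0.10 | 6.8% | 5.2% | 1.055 |

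**Step 5: power.** The power paragraph has no design effect and does not state the tested contrast. On one reading that gives more than 80% (survival of 70%, 75% and 80% in the three groups, 2-df test), power is 89% to 93% across risk groups. It becomes 86% to 92% at the ceiling DE of 1.075, so clustering does not threaten power on that reading.

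**Step 6: feasibility.** A hospital has at least one patient in a given cohort with probability 1 − (5/6)^10. That is about 1,174 of 1,400 sites, ample for a clustered sandwich variance. Only about 722 sites have two or more patients in a cohort.

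**The case against.** The strongest reply is that the plan does not ignore clustering. It raises the issue, commits to measuring it and lists site-level models. That stands: the treatment is conditional, and the first listed model, a grouping variable, is close to the correction proposed here.

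The second reply is that the check removes most of the harm. Even per cohort, an ICC of 0.10 is missed only 0.6% of the time, so the cases where clustering is wrongly dropped are mostly those where it matters little. If the check pools all patients, 0.05 is also caught. This stands too, and it is why the severity is low. It does not rescue the rule, because the plan neither defines small nor says at which level the check is made.

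A reader might infer that the harm is greatest when risk groups are compared, because each hospital then contributes 10 patients: 1 + 9 × 0.05 = 1.45, for a type I error of 10.4%. The documents do not support that. They plan six separate analyses and no formal test between cohorts. The formula would also be wrong for a difference between cohorts, since a hospital's shared effect enters the two cohorts with opposite signs. With exposure set by hospital, DE = 1 + ICC × (E[(n1 − n2)²]/E[n1 + n2] − 1). If each patient falls in a given cohort with probability p, both expectations equal 20p, so DE = 1 at any ICC. Two simulations gave type I errors of 5.0% and 5.2% at ICC 0.05. If exposure was instead set independently for each hospital and cohort, the figure was 6.2%, in line with the within-cohort results.

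Extending the full argument to Aim 2 is also tempting. Its patients came through a registry's rapid case ascertainment, not hospital sampling. Treating site is not among its listed covariates, and the number of sites is not given, so no size can be stated.

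**Conclusion.** The concern holds in a limited form. The primary Aim 1 analysis may drop a dependence built into the sampling, on a judgement with no stated criterion. If that judgement is made per cohort, it would miss an outcome ICC of 0.05 about one time in three. The resulting intervals would be about 0.3% to 4% too narrow, with type I error of about 5.0% to 5.9%. The upper end requires surveillance frequency to be set entirely by the site, which the documents do not claim.

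These figures rest on assumed ICCs, on a one-sided 5% test as the check, and on patients falling at random over the six cohorts. If the purposeful sampling concentrates a hospital's patients in fewer cohorts, m rises and so does the effect. Severity is low; the case for acting is that the correction is nearly free and removes a data-dependent choice.

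**What to change.** State in advance that all Aim 1 modified Poisson, Cox and Fine-Gray models use sandwich standard errors clustered on facility, and delete the rule that drops clustering when variation is small. Keep the fixed-effect and random-effect site models as sensitivity analyses. The fixed-effect model is a poor primary choice here because only about 722 sites per cohort have two or more patients, and a site with one patient gives no within-site comparison. Report the estimated ICCs for surveillance frequency and outcomes as description, not as a gate. In Aim 2, cluster by treating site only if it is recorded.

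The cost is one software option and a sentence in the plan. The unique facility identifier is already among the Aim 1 covariates, so no new data are needed. Point estimates do not change. If the true ICC is near zero, the intervals hardly move; otherwise they widen slightly, as they should.

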- High-risk prostate cancer (defined by clinical stage \geq T3, PSA >20, or Gleason 8-10): most aggressive type of prostate cancer. Recurrence risk is ~50%.⁷ Two cohorts will be examined separately, 5) those treated with **initial prostatectomy**, and 6) those treated with **initial radiation**.

[figure not shown]
The objective of this aim is to quantify the potential benefits (survival) and harms (procedures/tests, treatments) of different PSA surveillance frequencies in the 6 patient groups, which are currently unknown. It is intuitive that more frequent surveillance will lead to more findings of elevated PSA, thus leading to more downstream procedures and tests, and treatments; with unclear survival benefit. The *rationale* for this aim is that successful completion of the proposed research will contribute novel, currently unavailable, data to inform patient decision-making.

Comparators [RQ-5]: We selected our comparators of surveillance frequency based on published recommendations and by engaging diverse stakeholders (including clinicians who specialize in prostate cancer care). The three most common surveillance frequencies in clinical

practice are every 3, 6, or 12 months. In each of the 6 patient groups, patient outcomes of every 3 vs. 6 vs. 12 month surveillance will be directly compared. We will define our surveillance groups based on the number of PSA tests patients receive during the first year following completion of prostatectomy or radiation therapy (Figure) – using an “intention to treat” approach – and analyze patient outcomes from Years 2-10. Operationally, we will compare the outcomes of patients who have 1 vs. 2-3 vs. ≥ 4 PSA tests within the first year. We selected this timeframe as we believe that these patterns would be reflective of the physician’s intended surveillance schedule as opposed to later years which may be more reflective of patient adherence to surveillance recommendations.

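### The early-treatment sensitivity analysis excludes patients on a likely consequence of frequent testing: it understates treatment in that group and can bias recurrence and survival either way

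*Combined protocol and SAP*

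**What the plan says.** Exposure is fixed early. Under Comparators in Specific Aim 1, "we will compare the outcomes of patients who have 1 vs. 2-3 vs. ≥ 4 PSA tests within the first year". The approach is described as "intention to treat", and the plan will "analyze patient outcomes from Years 2-10".

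The last paragraph of Aim 1's Potential problems and alternative strategies deals with patients treated before they meet the official definition of recurrence. It does three things:

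- It will measure how common this is and "whether this prevalence is similar or different in the comparison groups".
- In the primary analysis, "we will assess outcomes (procedures, treatments) regardless of whether patients received treatments before meeting official definition of recurrence". The reason given is "because this is likely the result of patient/physician anxiety caused by frequent PSA surveillance testing".
- It then adds, as a sensitivity analysis, that "we will exclude patients who received treatment before meeting official definition of recurrence".

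The exclusion has no stated time limit, and the plan does not say which outcomes it applies to. The selection it creates is not discussed.

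**The concern.** A comparison that follows groups defined in year 1 should not let later events decide who is in them. Here the later event is, on the plan's own reasoning, a likely effect of the exposure. Unequal removal from the groups is therefore to be expected, and the remaining patients are no longer comparable in the way the year 1 definition intended.

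Treatment for recurrence is the outcome most directly affected. It is a secondary outcome, and treatments are among the harms that Aim 1 sets out to quantify. The exclusion removes only treated patients. Time to recurrence and overall survival are affected less directly, through the risk profile of those removed.

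A sensitivity analysis is read as a test of robustness. With this one, a difference from the primary result could come from selection alone, and agreement would give little reassurance.

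**Working it through.** **Inputs from the documents.** Recurrence risk is below 10% (low risk), about 30% (intermediate) and about 50% (high), from the Aim 1 Introduction. Ten-year overall survival is 70-80%, from Statistical power; 25% mortality is the midpoint. The documents give no early-treatment prevalence and no estimate of the effect of the exclusion, so there is no figure of the plan's to reproduce.

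**Assumptions.** e is the share treated early, T the total share treated, R the recurrence risk, and q the share of early-treated patients who would have recurred. All values of e, q and T are assumed. Pairs are given as ≥4 tests vs 1 test, and ratios are in that order.

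**1. Treatment for recurrence.** After exclusion the treated share is (T − e)/(1 − e). This is below T by e(1 − T)/(1 − e), so it is always too low within a group when e > 0 and T < 1.

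- *Equal treated share of 35%, e = 10% vs 2%:* (0.35 − 0.10)/0.90 = 27.8% vs (0.35 − 0.02)/0.98 = 33.7%. The ratio is 0.825, and the truth is 1.
- *Whole excess is early treatment, with 20% of the others treated:* the true shares are 0.10 + 0.90 × 0.20 = 28.0% vs 0.02 + 0.98 × 0.20 = 21.6%, ratio 1.296. After exclusion they are 20% vs 20%, ratio 1.000.

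Over other assumed prevalences:

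| e (≥4 vs 1) | Equal 35% treated: ratio shown | Whole excess early: true ratio → ratio shown |
|---|---|---|
| 5% vs 1% | 0.920 | 1.154 → 1.000 |
| 10% vs 2% | 0.825 | 1.296 → 1.000 |
| 15% vs 5% | 0.745 | 1.333 → 1.000 |

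**2. Recurrence.** Suppose the true risk R is the same in both groups. After exclusion it is (R − e·q)/(1 − e). This equals R when q = R, falls below R when q > R, and rises above R when q < R. With e = 15% vs 5%:

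| R | q | ≥4 tests | 1 test | Ratio |
|---|---|---|---|---|
| 50% | 1.00 | 41.2% | 47.4% | 0.87 |
| 50% | 0.50 | 50.0% | 50.0% | 1.00 |
| 50% | 0.25 | 54.4% | 51.3% | 1.06 |
| 30% | 1.00 | 17.6% | 26.3% | 0.67 |
| 30% | 0.30 | 30.0% | 30.0% | 1.00 |
| 30% | 0 | 35.3% | 31.6% | 1.12 |

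For example, at R = 50% and q = 0.25: (0.50 − 0.0375)/0.85 = 54.4% and (0.50 − 0.0125)/0.95 = 51.3%. In the low-risk cohorts, 15% early treatment with q = 1 is impossible, because (0.10 − 0.15)/0.85 is negative. If e is 5% in both groups and q is the same, the ratio is 1.000 at every q.

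**3. Overall survival.** The same form applies, with 25% mortality in both groups and e = 10% vs 2%. If early-treated mortality is 35%, the groups show (0.25 − 0.035)/0.90 = 23.9% vs (0.25 − 0.007)/0.98 = 24.8%, a false difference of −0.9 points. At 25% the difference is 0. At 15% it is 26.1% vs 25.2%, or +0.9 points.

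**The case against.** The best defence is that the plan already does most of what is needed. The primary analysis keeps these patients, and early-treatment prevalence will be compared between groups, which helps a reader interpret the exclusion. The plan says only that the cause is likely to be testing-related anxiety, so unequal prevalence is something it will measure and not an established fact. This stands, and it is why the severity is low. But measuring the imbalance reveals the selection without repairing it.

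A second defence is that the exclusion is informative. If excess treatment disappears when early-treated patients are removed (1.296 to 1.000), that shows where the excess lies. This is fair, but reporting early and later treatment separately in all patients gives the same information without presenting it as a robustness check.

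Third, a composite is not neutral. If early treatment is unrelated to recurrence risk, with R = q = 30% and e = 15% vs 5%, the composite risk R + e(1 − q) is 40.5% vs 33.5%, ratio 1.21, where exclusion gives 1.00. This also stands, so the composite should not be the only alternative.

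A reader might go further and infer that the exclusion removes future recurrences and so favours frequent surveillance in a known direction. The documents do not support that for recurrence. They do not say these patients would have recurred. They attribute the treatment to anxiety, and the Aim 1 Introduction notes that false-positive PSA results are much more common after radiation. Even with q = 0.8 at R = 50% and e = 10% vs 2%, the comparison depends on the alternative. If early-treated patients were kept but coded as non-events, the ratio would be (0.50 − 0.08)/(0.50 − 0.016) = 0.868; exclusion gives 0.945, a move against frequent testing.

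**Conclusion.** The concern holds in a limited form. The sensitivity analysis selects on a post-exposure event that the plan itself regards as a likely effect of the exposure.

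For treatment for recurrence, if early treatment is more common with frequent testing, the treated share in that group is understated by construction. How far the between-group ratio moves depends on e and T. In the assumed cases above, the shown ratio is 0.745 to 0.920 when the truth is 1, and a true excess of 15% to 33% disappears when it consists wholly of early treatment.

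For recurrence and overall survival, bias is possible but its sign is not determined, because it turns on whether early-treated patients are at higher or lower risk than the rest of their group. No bias arises if prevalence and risk are equal across groups. The sizes rest on assumed prevalences that the documents do not supply. The primary results are not affected.

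**What to change.** Make the main sensitivity analysis one that keeps all patients.

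- **Time to recurrence:** report two versions, one with early treatment as a competing event and one with a composite event, the earlier of official recurrence or treatment for suspected recurrence. Show both beside early-treatment prevalence by group.
- **Treatment for recurrence:** do not use the exclusion as a robustness check. Report early treatment and treatment after official recurrence as separate components in all patients.
- **If the exclusion is kept:** label it as conditioned on a post-exposure event, and state the outcomes to which it applies.

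The cost is SAP wording and a few extra tables. PSA dates and results and treatment dates are already to be abstracted (Outcomes), and Fine and Gray competing-risk methods are already planned (Data Analysis). The downside is that the composite mixes confirmed with suspected recurrence and would overcount recurrence if early treatment is driven by anxiety, which is why both versions should be shown.
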